9.1 Criteria for Safety Assessment

Vital sign monitoring, physical examination (swelling, tenderness, range of motion, and pain), and laboratory evaluations will be carried out to determine the safety of the investigational product. When an adverse event occurs, the type, the severity, dates of the onset and resolution of the adverse event, and the relationship between the investigational product and the adverse event will be investigated and documented on the case report form.

Causality of the adverse events will be determined according to the following criteria:

 \checkmark Not related: the adverse experience is definitely not related to the investigational product

✓ Unlikely: there are other, more likely causes and the investigational product is not suspected as a cause

 \checkmark Suspected, reasonable possibility: the direct cause and effect relationship between the drug and the adverse event has not been demonstrated but there is a reasonable possibility that the event was caused by the drug.

 \checkmark Probable: there probably is a direct cause and effect relationship between the adverse event and the investigational product

CONFIDENTIAL: These all contents herein are the sole property of MEDIPOST Co., Ltd. Any reproduction or distribution of this document without the written consent of MEDIPOST Co., Ltd is prohibited. Copyright © 2017 MEDIPOST Co., Ltd

Certainty of causal relationship between the adverse event and the investigational product (or any other reasons – progression of an underlying disease, concomitant therapy, etc.) will be determined on the basis of how well the adverse event could be explained in light of the following factors:

✓ Known pharmacological effect and mechanism of the investigational product

 \checkmark Similar events previously reported for the investigational product or other substances of the same class

✓ Drug reactions frequently reported with similar medications

 \checkmark Events that are temporally associated with the investigational product (events that are resolved once the drug is discontinued but reappear with the next administration)

The study will be under ongoing periodic reviews by an assigned Independent Data Monitoring Committee (IDMC). An IDMC will independently review data on a periodic basis as detailed in the IDMC charter. Serious AEs will be reported to the IDMC as outlined in the IDMC charter. The IDMC will make recommendations to the Sponsor as to whether the trial should be revised or closed.

10 Statistical Analysis

10.1 Analysis Populations

10.1.1 Safety Population

The safety analysis for all clinical and laboratory adverse experiences will be based on all enrolled patients who are administered the investigational product.

10.1.2 Efficacy Population

The efficacy population will be defined as all patients who met the eligibility criteria and received at least one dose of the investigational product, and had been assessed at least once for at least one efficacy endpoint.

10.2 Analysis of Safety Variables and Statistical Evaluation

10.2.1 Safety Variables

All adverse events will be coded according to the latest version of MedDRA and the classification according to the System Organ Class of MedDRA using preferred term.

All adverse events will be summarized and analyzed.

CARTISTEM®

page 41 of 137

CONFIDENTIAL: These all contents herein are the sole property of MEDIPOST Co., Ltd. Any reproduction or distribution of this document without the written consent of MEDIPOST Co., Ltd is prohibited. Copyright © 2017 MEDIPOST Co., Ltd

Serious adverse events and drop-out patients due to adverse events will be described in details.

Descriptive statistics including means, medians, SD (standard deviation), minimum and maximum will be used to present the other safety endpoints, laboratory tests including routine hematology and chemistry, thrombin generation (PT and aPTT), vital signs, autoimmune disease test (T-cell subset) and ECGs. For laboratory data, the number of subjects who deviated from the normal range will be presented for each analyte, by visit, and by dosage phase. The results will be also classified into normal, decreased, or increased in relation to the normal range.

10.2.2 Analysis of Safety Endpoints

Analysis of the adverse events, adverse drug reactions, and serious adverse events will be presented with number of case (# of subject who experienced), number of adverse events, and percentage.

Analysis of the adverse events will include the severity, the seriousness and the relationship with the study medication. It will be presented with number of event and percentage.

Incidence rates of the adverse events including adverse drug reactions and serious adverse events occurred in each dose group will be presented with frequency, percentage, and 95% confidence interval of the rates. Homogeneity between dose groups will be analyzed using person's chi-square test or Fisher's exact test.

Incidence rates of the adverse drug reaction by SOC between two dose groups will be analyzed for homogeneity using pearson's chi-square test or Fisher's exact test.

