Efficacy Evaluation	Primary efficacy outcome parameters will be the postoperative changes in subjective knee function as assessed by IKDC (International Knee Documentation Committee) score at 12 months. For secondary efficacy outcome parameters, patients will answer questionnaires for pain (visual analogue scale, VAS), knee specific outcome instruments (Lysholm knee scoring, and KOOS [Knee injury and Osteoarthritis Outcome Score]). Structural information will be gathered using high-resolution (1.5 or 3 Tesla) magnetic resonance imaging (MRI).

page 7 of 137

CONFIDENTIAL: These all contents herein are the sole property of MEDIPOST Co., Ltd. Any reproduction or distribution of this document without the written consent of MEDIPOST Co., Ltd is prohibited. Copyright © 2017 MEDIPOST Co., Ltd.

Statistical Methods	General: all safety and efficacy endpoints will be presented for each dose cohort as well as for all patients combined. For safety evaluation, statistical homogeneity between dose groups will be performed. For efficacy evaluation, statistical comparison (difference) between dose groups will be performed.
	1) Safety Safety will be demonstrated with 95% confidence intervals. Adverse events, adverse drug reactions, serious adverse events, and drop-out patients due to AE will be presented with frequency and percentage. Homogeneity between dose groups will be analyzed using person's chi-square test or Fisher's exact test. Descriptive statistics including means, medians, SD (standard deviation), minimum and maximum will be used to demonstrate the other safety endpoints.
	2) Efficacy Symptom improvement from the outcome instruments will be demonstrated with means and standard deviations. Efficacy results will also be analyzed for statistical significance using change from baseline at each efficacy endpoint. Statistical difference of continuous variables and categorical variables between dose groups will be compared using t-test and Fisher's exact test, respectively.
Rationale for Study Population and Number of Patients	CARTISTEM [®] is administered to the defective joint cartilage region by open surgery. Due to ethical considerations, it is not possible to conduct this type of procedure in a healthy subject. Therefore, no studies in healthy subjects will be performed.

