6.3 Number of Subjects

1) Estimated Number of Patients

This study requires 12-18 patients (6-9 patients per arm depending on rate of DLT) for two different dose ranges (Dosage A: defect sizes of 2-5 cm² and Dosage B: defect sizes of above 5 cm²).

2) Target Number of Subjects and Rationale

This is a phase I/IIa clinical trial to evaluate safety and exploratory efficacy of the investigational drug product. Therefore, it is not considered critical to base the number of subjects on formal statistical power calculations. Six patients at each dose cohort enrolled sequentially are considered sufficient for this study. This study will be performed with two dose ranges, on the basis of existing pre-clinical test results. Initially, 6 patients with defect sizes of 2-5 cm² will be enrolled in Dosage A. If no DLT is seen during Dosage A, another 6 patients with larger defect sizes (above 5 cm²) will be recruited for Dosage B of the study. There could be a need for an intermediate dose or up to 6 additional patients, based on the rate of DLT seen.

CARTISTEM®

page 21 of 137

CONFIDENTIAL: These all contents herein are the sole property of MEDIPOST Co., Ltd. Any reproduction or distribution of this document without the written consent of MEDIPOST Co., Ltd is prohibited. Copyright © 2017 MEDIPOST Co., Ltd.

1) Initial Administration Dosage and Rationale

It is somewhat well understood by developers and regulators of living cell therapies that for products like CARTISTEM[®] administered locally into an anatomical defect there is no simple extrapolation of a safe starting dose in humans based primarily upon body surface area calculations derived from animal studies.

In addition, dose determinations in this clinical setting should take into account the surface area of the cartilage defect such that all NOAEL values should be converted into a unit quantity (cells/cm²) at the application site. This approach applies to most therapeutics administered into anatomical compartments that have little subsequent distribution outside of the compartment; it is recommended that doses are normalized between species according to the compartmental volumes and amount of the therapeutic product.

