8.4.3 Evaluation of Adverse Events & Toxicity

Any adverse events (AE) or toxic reactions of each participating subject will be evaluated throughout the course of the study and at each follow up visit (from Day -2 to the end-of-study visit). Any adverse events or serious adverse events will be managed, investigated, and reported according to the procedures described in the following sections:

✓ Adverse Events

When an adverse event is either observed by the investigator or reported by a subject, the investigator, regardless of the relationship of the AE to the investigational product, will record name and type of the adverse event, the severity, dates of onset and resolution of the event, the investigator's opinion on the relationship between the investigational product and the adverse event, and whether or not the event was an SAE (serious adverse event) on the case report form (CRF).

The principal investigator or the trial coordinator will carry out follow-up observations for all subjects with adverse events until the symptoms subside and the abnormal clinical test results are returned to normal, or until a satisfactory explanation can be given for the observed changes. If and when there is such a request from the sponsor, a progress report on the adverse event will be submitted to the trial coordinator.

✓ Serious Adverse Events

A serious adverse event is defined as any untoward medical occurrence at any dose that causes death, life-threatening condition, in-patient hospitalization or prolongation of existing hospitalization, persistent or significant disability/incapacity, a congenital anomaly/birth defect, or another important medical event (see below).

CARTISTEM®

CONFIDENTIAL: These all contents herein are the sole property of MEDIPOST Co., Ltd. Any reproduction or distribution of this document without the written consent of MEDIPOST Co., Ltd is prohibited. Copyright © 2017 MEDIPOST Co., Ltd

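### Section 10.2.2 breaks adverse events down by severity as events and an undefined percentage, so the number of patients with a severe (Grade 3 or higher) event is not a planned output.

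*Combined protocol and SAP*

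**What the plan says.** Section 10.2.2 uses different units for different safety summaries.

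- AEs, ADRs and SAEs overall are "presented with number of case (# of subject who experienced), number of adverse events, and percentage".
- The next paragraph turns to subdivisions: "Analysis of the adverse events will include the severity, the seriousness and the relationship with the study medication". It continues: "It will be presented with number of event and percentage". The subject count is gone, and the base of the percentage is not named.
- Incidence rates by dose group, for AEs including ADRs and SAEs, are "presented with frequency, percentage, and 95% confidence interval of the rates". Homogeneity tests follow, and ADRs are also compared by system organ class. None of this is split by severity.

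The synopsis (Statistical Methods) does not mention severity: "Adverse events, adverse drug reactions, serious adverse events, and drop-out patients due to AE will be presented with frequency and percentage". Section 10.2.1 promises detailed description of SAEs and of patients who drop out because of AEs.

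A patient denominator exists. Under Section 10.1.1 the safety analysis "will be based on all enrolled patients who are administered the investigational product". Section 6.3 puts the size at 6 to 9 patients per dose group and 12 to 18 in total. Section 8.4.3 has the investigator record severity for every event.

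**The concern.** In a first-phase safety study, readers want to know how many treated patients had a severe event, and how many had one judged related to the product. Section 10.2.2 gives the patient as a unit for the overall categories but drops it for severity. Subject counts for SAEs and ADRs are planned in their own right, which largely covers seriousness and relationship. Severity has no such backup.

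Events cluster within patients, so a count of severe events does not show how many people were affected. In groups of 6 to 9, one patient with three severe events and three patients with one each are different findings, and they bear differently on the comparison of the two dose groups. An undefined percentage adds a second difficulty, because its meaning depends on a denominator that the table programmer would have to choose.

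**Working it through.** The plan states no figure to reproduce. The check has two parts: whether any section supplies the patient count, and what the event-level display can show.

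**1. Search for the patient count**

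| Place | Planned output | Patients by severity? |
|---|---|---|
| 10.2.2, overall AE/ADR/SAE | subjects, events, percentage | No severity split |
| 10.2.2, severity/seriousness/relationship | events, percentage | No subject count |
| 10.2.2, incidence with 95% CI | AE, ADR, SAE by dose group | No severity split |
| 10.2.1 | detail on SAEs and AE drop-outs | Only if serious or leading to drop-out |
| Synopsis, Statistical Methods | AE, ADR, SAE, AE drop-outs | Severity not mentioned |
| 6.5 and 6.6 | DLTs counted by patient for escalation and MTD | Narrower than any Grade 3+ event; no DLT table in Section 10 |
| Appendix 5 | board reviews aggregate and individual safety data | No table specified |

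The DLT definition in 6.6 has two limbs: two or more local signs at Grade 3 or above at one visit, or an ADR of CTCAE Grade 3 or above, subject to listed exceptions. A single Grade 3 local sign, or a Grade 3 AE judged unrelated, need not be a DLT. The DLT count therefore does not stand in for the count of patients with any Grade 3+ AE.

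**2. What three severe events can mean in a 6-patient dose group** (the count of three is assumed; 6 is the planned group size)

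Proportion = x/n. The exact (Clopper-Pearson) 95% limits are the 2.5% quantile of Beta(x, n−x+1) and the 97.5% quantile of Beta(x+1, n−x).

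| Patients affected | x/n | Percentage | Exact 95% CI |
|---|---|---|---|
| 1 | 1/6 | 16.7% | 0.4 to 64.1% |
| 2 | 2/6 | 33.3% | 4.3 to 77.7% |
| 3 | 3/6 | 50.0% | 11.8 to 88.2% |

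All three rows give the same entry, 3, in the planned event table.

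**3. Effect of the unstated denominator** (assumed: 12 patients, three of whom have one Grade 3 event each, and every patient also reports m mild events)

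- By patient: 3/12 = 25.0%, exact 95% CI 5.5 to 57.2%, whatever the value of m.
- By event, if the denominator is all events: 3/(3 + 12m). For m = 2 this is 3/27 = 11.1%. For m = 5 it is 3/63 = 4.8%.
- If the denominator is patients but the numerator is events, the figure is events per patient. With m = 2 the 27 events over 12 patients give 27/12 = 225%, which is not the proportion of patients affected.

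So neither denominator yields the patient count.

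**The case against.** The strongest reply is that little is hidden in a study this small. The number of severe events is printed beside the percentage, so three severe events show as three however many mild ones are recorded. Subjects with any AE, ADR or SAE are counted, SAEs and AE drop-outs are described in detail, and DLTs are counted by patient. Escalation, halting and the MTD rest on those DLT counts, so no rule in the protocol uses the severity table. This all stands and limits the weight of the point, but it does not supply the missing count.

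A reader might infer more than the text supports:

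- **That the severe share is certain to shrink.** This depends on the denominator being all events. That is a natural reading, but the section does not say so.
- **That severity crossed with relationship is reported by event.** The section lists severity, seriousness and relationship as three items and describes no cross-table.
- **That the planned 95% CI cannot be applied.** That interval belongs to the incidence rates in the following paragraph. None is planned for severity, so there is no conflict.
- **That the safety picture would be falsely mild.** The printed event counts, the SAE descriptions and the patient-level DLT counts make that too strong.

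It is also fair to say that Sections 8.4.3 and 10.2.2 name no severity scale. Grade 3 or higher is borrowed from CTCAE v4.0, which the protocol uses in its DLT definition and appends.

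**Conclusion.** The point holds as a gap in the planned presentation, not in data collection. For its primary objective the plan gives no count of patients by severity. As a result, three severe events in a group of six are compatible with anything from 16.7% to 50.0% of patients affected. That range is arithmetic from the planned group size and an assumed three events.

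The fall from 25% to 11.1% or 4.8% is conditional. It needs the all-events denominator and the assumed numbers of mild events, and it shows the mechanism without estimating its size in this trial. No escalation or halting decision is affected. The change is worth making because the patient-level table is more informative than the event-level one and costs almost nothing.

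**What to change.** Replace the event-only sentence in Section 10.2.2, as it applies to severity, with:

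> Severity (CTCAE v4.0 grade, the scale already used for DLT) will be presented as number and percentage of treated patients by worst grade, for all AEs and for related AEs, by dose group and combined, with exact 95% CI; event counts will be shown in addition, with the denominator of any event percentage stated.

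This makes three changes: it adds the patient count, names the severity scale, and defines the event percentage. The cost is one sentence and one table shell. Severity is already recorded for each event and the treated-patient denominator is already defined. The sponsor should confirm that the case report form's severity field holds a CTCAE grade, since Section 8.4.3 does not say so. No dose, schedule, escalation or halting rule changes.

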10.3.2 Analysis of Efficacy Endpoints

The descriptive statistics of the categorical variables will be presented with percentage and frequency and that of the continuous variables such as mean, median, standard deviation, and interquartile range. The primary efficacy endpoint will be analyzed using the t-test. As for the secondary efficacy endpoints, differences of the continuous variables and the categorical variables between the two groups will be analyzed using the t-test and Fisher's exact test, respectively.

CONFIDENTIAL: These all contents herein are the sole property of MEDIPOST Co., Ltd. Any reproduction or distribution of this document without the written consent of MEDIPOST Co., Ltd is prohibited. Copyright © 2017 MEDIPOST Co., Ltd

11 Rehabilitation Protocol

All patients must participate in the following standardized rehabilitation program after receiving treatment. Rehabilitation program will vary according to the defect location of each subject.

Stage 1- Proliferative Phase (Week 1 to 6)

Femoral Condyle Defect

	PRIMARY GOALS
	DO NOT OVERLOAD GRAFT
	INCREASE TIBIOFEMORAL AND PATELLOFEMORAL MOBILITY
	RESTORE QUADRICEPS CONTROL
BRACE	• Knee immobilizer with ambulation, until good quads control/SLR (approximately Week 3 to 6)
GAIT	Heel-toe TDWB with crutches
ROM	• Full AROM and gentle AAROM.
	 CPM ≥ 6 to 8 hours daily for 6 weeks. Start at 0-40 degrees, progress range as tolerated.
	• Goal: minimum 90 degrees flexion for the first 2 weeks, 110 degrees for the next 4 weeks (the 6 week time point of post-op)
THEREX	• Quad sets, SLR in knee immobilizer as needed, leg curl/heel slides, hip abduction
	 Stationary bicycle with no resistance once 90 degrees knee flexion obtained (~ 4 weeks).
	 90 degree leg dangle hourly to improve ROM
THERAPY	 Gentle multi-directional patella mobilization starts immediately after surgery. Cryotherapy and compression stockings/TEDS for swelling and pain control. E-stim for VMO/quadriceps muscle re-education/biofeedback encouraged
	early after surgery if needed.
	 Gentle massage/deep friction to hamstring insertions, suprapatellar quadriceps, medial/lateral gutters, and infrapatellar fat pad region at 2-3 weeks post-op.
	 Pool therapy recommended 2-3 weeks post-op to enhance motion.
	• Foot merapy recommended 2-5 weeks post-op to emiance motion.

page 44 of 137

Femoral Condyle Defect

PRIMARY GOALS DO NOT OVERLOAD GRAFT INCREASE TIBIOFEMORAL AND PATELLOFEMORAL MOBILITY RESTORE QUADRICEPS CONTROL

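### Safety homogeneity between the two dose cohorts is assessed only by a test of difference at 6 to 9 patients each, with no interval for the difference (minor; reporting only)

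*Combined protocol and SAP*

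**What the plan says.** The synopsis (Statistical Methods, General) gives safety and efficacy different between-cohort aims: "For safety evaluation, statistical homogeneity between dose groups will be performed. For efficacy evaluation, statistical comparison (difference) between dose groups will be performed". Section 10.2.2 gives the safety method: "Homogeneity between dose groups will be analyzed using person's chi-square test or Fisher's exact test". It repeats the approach by system organ class: "Incidence rates of the adverse drug reaction by SOC between two dose groups will be analyzed for homogeneity".

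Some interval reporting is already planned. The synopsis says "Safety will be demonstrated with 95% confidence intervals" and that "all safety and efficacy endpoints will be presented for each dose cohort as well as for all patients combined". In section 10.2.2 the 95% intervals attach to the incidence rate within each dose group. Neither place gives an interval for the between-cohort difference, a margin, a significance level for the homogeneity test, or a rule for choosing between the two tests.

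On size, section 6.3 says "This study requires 12-18 patients (6-9 patients per arm depending on rate of DLT) for two different dose ranges", and adds that the number was not based on a formal power calculation. For secondary efficacy categories, section 10.3.2 names Fisher alone: "differences of the continuous variables and the categorical variables between the two groups will be analyzed using the t-test and Fisher's exact test, respectively".

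**The concern.** The stated safety aim is sameness, but the tool has equality as its null hypothesis. Failing to reject equality supports sameness only if the test would probably have rejected had the cohorts differed materially. At 6 to 9 patients per cohort it would not.

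Safety is the primary objective, and this test is the only between-cohort safety inference in the plan. The report would therefore carry a homogeneity p-value and no figure for how large a cohort difference the data leave open.

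**Working it through.** **Inputs.** Cohort sizes of 6 to 9 come from section 6.3. No significance level is stated, so two-sided 0.05 is assumed, in line with the 95% intervals. The plan gives no figure of its own to reproduce. All possible tables were enumerated. Differences are Dosage B minus Dosage A, in percentage points.

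**1. When Fisher rejects at 6 v 6.** There are 7 × 7 = 49 tables. For 0/6 v b/6 the two-sided p-value is 2 × C(6,b)/C(12,b) for b of 2 or more.
- 0/6 v 4/6: 2 × 15/495 = 0.061, not significant.
- 0/6 v 5/6: 2 × 6/792 = 0.015, significant.
- 1/6 v 5/6: 2 × (36 + 1)/924 = 0.080, not significant.
- 1/6 v 6/6: 2 × 6/792 = 0.015, significant.

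The rejecting tables are 0 v 5, 0 v 6, 1 v 6 and their mirrors. That is 6, so 49 − 6 = 43 are non-significant.

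**2. What a non-significant table leaves open.** For each table, an exact unconditional 95% interval for the risk difference was found by inverting two one-sided score tests at 0.025. The p-value was maximised over the unknown common-nuisance rate, on a 1-point grid. The larger absolute limit is the largest difference still compatible with the data.

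| Cohort sizes (A v B) | Fisher non-significant | Smallest of these largest differences |
|---|---|---|
| 6 v 6 | 43 of 49 | 45 points |
| 9 v 6 (and 6 v 9) | 50 of 70 | 45 points |
| 9 v 9 | 72 of 100 | 33 points |

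Hand check at the most favourable 6 v 6 table, 0/6 v 0/6: if A's true rate is 0 and B's is d, the chance of seeing no event is (1 − d)^6. At d = 0.45 this is 0.55^6 = 0.0277, above 0.025, so 45 points is not excluded. At d = 0.46 it is 0.54^6 = 0.0248.

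Identical observed cohorts at 6 v 6 give ±45 (0/6 each), ±50 (1/6), ±54 (2/6) and ±57 (3/6).

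**3. Chi-square at these sizes.** With cohorts n and m, N = n + m and s events in total, the smallest expected count is min(n,m) × min(s, N − s)/N, which is at most min(n,m)/2. Its largest possible value is 6 × 6/12 = 3.0 at 6 v 6, 6 × 7/15 = 2.8 at 9 v 6, and 9 × 9/18 = 4.5 at 9 v 9. The usual condition of at least 5 is not met at any planned size.

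**4. Does the choice of test matter?** Uncorrected Pearson chi-square and Fisher give different verdicts in 10 of 49 tables at 6 v 6. At 0/6 v 3/6, chi-square = 12 × (0 × 3 − 6 × 3)²/(6 × 6 × 3 × 9) = 4.0, p = 0.0455. Fisher gives 2 × 20/220 = 0.18. With a continuity correction, none of the 49 tables differ.

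**5. Which interval method.** The Newcombe interval excludes zero on exactly the tables where uncorrected chi-square rejects: 16 of 49 at 6 v 6, 22 of 70 at 9 v 6 and 38 of 100 at 9 v 9. Offering it as interchangeable with the exact interval would restore the decisions of the method being removed.

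**The case against.** The case for leaving the text alone is reasonable. The trial is exploratory and its small size is openly stated. Homogeneity is ordinary usage for a test whose null is equal proportions. Rates per cohort with 95% intervals are planned, so a reader seeing 0/6 with an upper limit of 46% already sees how little is known. All of this stands, and it limits the severity. It does not supply the size of the between-cohort difference: two separate intervals compared by eye are not an interval for the difference.

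Three stronger readings are tempting, and none is supported.

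- A reader might infer that p above 0.05 will be declared proof of similar safety. The plan states no such rule; it only leaves that reading open.
- A reader might infer that dose decisions depend on this test. They do not: sections 6.5 and 6.6 base escalation, halting and the MTD on DLT counts, with safety review by the IDMC (section 9.1, Appendix 5).
- A reader might point to 0/6 v 4/6, where Fisher gives p = 0.061 but the exact unconditional interval runs from +11 to +95, and say the test misses what an interval shows. That contrasts a conditional with an unconditional method. Barnard's unconditional test gives a two-sided p of about 0.02 there.

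The chi-square point has a limit too. Section 8.5 allows replacement of withdrawn patients and section 10.1.1 counts everyone treated, so a cohort could exceed 9 and the 4.5 ceiling would rise.

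**Conclusion.** The concern holds as a minor reporting point. A test of difference at 6 to 9 patients per cohort cannot support the homogeneity it is meant to assess. At 6 v 6 every one of the 43 non-significant Fisher tables is compatible with a true difference of at least 45 points; at 9 v 9 the figure is 33 points for all 72.

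These figures rest on an assumed two-sided 0.05, the exact unconditional interval described above, and the planned cohort sizes. They need no assumption about event rates. Low power as such is not the objection. Because the cohorts are enrolled in sequence and defined by defect size, no between-cohort summary, including the one proposed, isolates dose.

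**What to change.** In section 10.2.2 and the synopsis, replace the homogeneity sentences with:

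> The between-cohort summary for AE, ADR and SAE incidence is the Dosage B minus Dosage A risk difference with an exact unconditional 95% CI, alongside the per-cohort and pooled rates with 95% CIs. ADRs by SOC are presented as counts and percentages. The comparison is descriptive; cohorts are sequential and defined by defect size, so it does not isolate dose.

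Delete the chi-square option. If a p-value is kept, use Fisher's exact test only and state that non-significance is not evidence of similar safety. Name the exact unconditional interval alone, without Newcombe as an alternative.

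The cost is a few sentences and no new data. The downside is that the intervals will be wide, about ±45 to ±57 points for identical cohorts at 6 v 6, and that no p-value-based statement of similarity can be made.
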